### 2.4.2 Secondary

- OS will be measured from the time of initiation of SRS until death from any cause
- Local control rate of sites ablated by SRS will be measured both overall and by lesion
- Toxicity of SRS will be measured by NCI CTCAE version 4 following completion of SRS, but prior to erlotinib re-initiation.
- Toxicity of erlotinib will be graded using NCI CTCAE version 4.

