#### 4.3 Erlotinib Treatment Dosage and Administration

Erlotinib (Tarceva®) will be administered per standard of care. Of note, patients with EGFR mutation often require substantially less than the standard dose to achieve efficacy. Thus, while the study recommends a standard starting dose, patients with known intolerance at this dose, but known tolerance with efficacy at a lower dose will be allowed to initiate at that dose. Erlotinib will be taken once per day on an empty stomach (one hour before, or two hours after food).

At the time of enrollment into the study, patients may already be on erlotinib therapy. For these patients, it is recommended (but not required) that erlotinib be discontinued 3 days prior to the initiation of SRS (i.e., if last dose of erlotinib is on a Sunday, SRS can be administered on Thursday). The study recommends that erlotinib be restarted 3 days after the completion of SRS. At the investigator's discretion, erlotinib may be started sooner (or never discontinued) but not later. .

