### 7.1.2 Suspected Adverse Reaction (SAR)

A suspected adverse reaction (SAR) is any AE for which there is a *reasonable possibility* that the drug is the cause. *Reasonable possibility* means that there is evidence to suggest a causal relationship between the drug and the AE. A suspected adverse reaction implies a lesser degree of certainty about causality than adverse reaction, which means any adverse event caused by a drug.

Causality assessment to a study drug is a medical judgment made in consideration of the following factors: temporal relationship of the AE to study drug exposure, known mechanism of action or side effect profile of study treatment, other recent or concomitant drug exposures, normal clinical course of the disease under investigation, and any other underlying or concurrent medical conditions. Other factors to consider in considering drug as the cause of the AE:

- Single occurrence of an uncommon event known to be strongly associated with drug exposure (e.g., angioedema, hepatic injury, Stevens-Johnson Syndrome)
- One or more occurrences of an event not commonly associated with drug exposure, but otherwise uncommon in the population (e.g., tendon rupture); often more than once occurrence from one or multiple studies would be needed before the sponsor could determine that there is *reasonable possibility* that the drug caused the event.
- An aggregate analysis of specific events observed in a clinical trial that indicates the events occur more frequently in the drug treatment group than in a concurrent or historical control group

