## **7.2 Documentation of non-serious AEs or SARs**

For non-serious AEs or SARs, documentation must begin from day 1 of study treatment and continue until the AE or SAR is resolved or returns to <grade 1 or baseline.

Collected information should be recorded in the Electronic Case Report Forms (eCRF) for that patient. Please include a description of the event, its severity or toxicity grade, onset and resolved dates (if applicable), and the relationship to the study drug. Documentation should occur at least monthly.

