## **7.3 SAEs or Serious SARs**

### **7.3.1 Timing**

After informed consent but prior to initiation of study medications, only SAEs caused by a protocol-mandated intervention will be collected (e.g. SAEs related to invasive procedures such as biopsies, medication washout, or no treatment run-in).

For any other experience or condition that meets the definition of an SAE or a serious SAR, recording of the event must begin from day 1 of study treatment and continue through the 30 day follow-up period after treatment is discontinued.

For any other experience or condition that meets the definition of a serious adverse event (SAE) or SAR, recording of the event must begin from day 1 of study treatment and continue through the 30 day follow-up period after treatment is discontinued.

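### Section 2.4.2 confines SRS toxicity to roughly the 0 to 3 days between SRS and erlotinib restart, so the reported proportion cannot count SRS effects that arise later

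*Combined protocol and SAP*

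**What the plan says.** Objective 2.2.3 is to describe the toxicity of SRS, with no time limit. The matching endpoint in 2.4.2 adds one: "Toxicity of SRS will be measured by NCI CTCAE version 4 following completion of SRS, but prior to erlotinib re-initiation". Section 6.9.4 names the CTCAE scale and nothing more.

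The closing event depends on 4.3. For patients already on erlotinib at enrollment, a hold before SRS is recommended but not required. On restart the section says "The study recommends that erlotinib be restarted 3 days after the completion of SRS", and then that "erlotinib may be started sooner (or never discontinued) but not later". Footnote 2 of the 6.1 table provides for patients who take erlotinib right through SRS. It also lets the post-SRS visit fall on the final radiation day.

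Collection is broader than the endpoint. The 6.1 table marks toxicity assessment as continuous. For non-serious events, 7.2 says "documentation must begin from day 1 of study treatment and continue until the AE or SAR is resolved or returns to" below grade 1 or baseline. For serious events, 7.3.1 has recording "continue through the 30 day follow-up period after treatment is discontinued". Section 6.8 makes every treated patient evaluable for toxicity, and 8.3 summarizes toxicity as proportions.

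**The concern.** The endpoint is narrower than the objective it serves. The numerator is limited to a few days at most, while the denominator is every treated patient. An SRS effect that first shows itself after restart falls outside the definition, although the event itself is on record. A reader of the trial report would take the SRS toxicity proportion as a description of SRS toxicity, when it describes only the immediate post-SRS interval. For patients who never stop erlotinib, the definition gives no usable interval at all.

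**Working it through.** The plan states no expected rate or precision for SRS toxicity, so there is no figure of its own to reproduce. The check is of dates, readings and counting.

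**Step 1: length of the interval.** Let day 0 be the day SRS finishes. Length = restart day − 0.

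- Restart at once (allowed by 4.3): 0 − 0 = 0 days.
- Restart as recommended in 4.3: 3 − 0 = 3 days.
- Counting full drug-free days: 4.3 illustrates the hold before SRS with "if last dose of erlotinib is on a Sunday, SRS can be administered on Thursday". With Sunday as day 0, Thursday is day 4. If the same counting were carried over to the restart, the length would be 4 days. The example concerns the pre-SRS hold only, so this is a possible reading, not a stated rule.
- Erlotinib never stopped: no restart day exists, so the length is undefined (either empty or unlimited).

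Counting 8 weeks from SRS completion as 56 days, the 3-day maximum is 3/56 = 5.4% of the time to a first 8-week visit. Over three such intervals it is 3/168 = 1.8%. These are shares of calendar time, not of events.

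**Step 2: the two readings of 2.4.2.**

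| | Onset window | Post-SRS visit (6.3.1) |
|---|---|---|
| Events that arise and resolve during fractionation (up to ten treatments in 4.2.2f) | excluded | can be noted |
| Patients continuing erlotinib | no closing event | have an assessment point |
| Effects first arising after restart | excluded | missed; the visit may be on day 0 |

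For patients who hold erlotinib, later effects are missed on both readings.

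**Step 3: effect on the proportion.** Let N be the patients treated, T those with an SRS effect, and E those whose effect 2.4.2 captures. The objective calls for T/N; the endpoint gives E/N. The shortfall is (T − E)/N. Since E cannot exceed T, this omission can only lower the proportion. With N = 40 (the planned size, assuming all are treated), each missed patient costs 1/40 = 2.5 percentage points. T − E is unknown: the documents give neither onset times for SRS effects nor the number of patients continuing erlotinib.

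**Step 4: does continuous collection repair this?** Only in part. The events exist in the database. But 7.2 asks for "its severity or toxicity grade, onset and resolved dates (if applicable), and the relationship to the study drug", and 7.1.2 says "Causality assessment to a study drug is a medical judgment made in consideration of the following factors". Neither section specifies a separate judgment on SRS. The erlotinib item in 2.4.2 gives a grading scale but no window and no relatedness rule. The plan therefore does not say in which table a post-restart event is counted.

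**The case against.** The best defense is that the split is deliberate. Objectives 2.2.3 and 2.2.4 separate SRS toxicity from the toxicity of erlotinib given after SRS, and assessing SRS before restart avoids dividing events between two treatments. That is a coherent purpose, and a pre-restart rate is worth keeping under a label that says what it is. It does not make that rate a description of SRS toxicity, and it does not work for patients who continue erlotinib.

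Several stronger readings are tempting and are not supported:

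- A reader might infer that later SRS events will be reported as erlotinib toxicity. No section says so. An event judged due to radiation could be marked unrelated to erlotinib; its placement is simply unstated.
- A reader might infer that no later event can be attributed to SRS. Sections 7.1.1, 7.1.2 and 7.3.1 also use wider terms covering study therapy, study treatment or protocol-mandated interventions, and the eCRF is not in the documents. What can be said is that a separate SRS attribution is not specified.
- Section 6.9.2 says treated areas inflame after SRS, but it concerns how treated lesions are judged for local control. It is not evidence of late CTCAE events.
- Of the 1 + 3 = 4 scheduled toxicity evaluations after SRS in the first 6 months, at least 3 fall after restart. This counts visits. With continuous assessment and at least monthly documentation (7.2), it measures neither lost data nor bias.

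One further limit stands: the 3-day text in 4.3 addresses patients on erlotinib at enrollment. For anyone not taking it then, no start interval is clearly given.

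**Conclusion.** The point holds as a matter of endpoint definition. For patients who hold and restart erlotinib, 2.4.2 covers about 0 to 3 days; for those who continue, it has no end. Following the plan as written yields an SRS toxicity proportion that cannot include effects arising after restart, and so does not deliver objective 2.2.3. Read as an onset window, it also leaves out events that come and go during fractionation.

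The direction of this omission is certain; the amount cannot be estimated. The conclusion rests on 2.4.2 being applied literally and on no other section giving a wider window; 6.9.4 is silent rather than in conflict. No adverse event is lost from collection. The endpoint is secondary and descriptive, and primary PFS, the sample size and ongoing safety review do not depend on it. The change is worth making because it is cheap.

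**What to change.** **Definition (2.4.2, and 6.9.4 by reference).** Count CTCAE v4 events with onset or worsening from the first SRS/ablation session that the investigator judges at least possibly related to SRS/ablation, regardless of erlotinib timing. The relatedness condition is needed because erlotinib's common effects would otherwise enter the SRS rate: in the two trials tabulated in 5.1.4, any-grade rash was 49.2% and 75%, and diarrhea 20.3% and 54%.

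**Window.** Use one fixed period after the last session, the same for all patients and served by existing visits, for example through the first 8-week visit. That visit is timed from erlotinib initiation at 56 ± 7 days, so 49 to 63 days. With restart 0 to 3 days after SRS, it falls 49 to 66 days after the last session. The window is therefore best written in days from the last session, with this visit as its assessment. Closing instead at 30 days after the last protocol treatment, as in 7.3.1, would make observation time depend on how long erlotinib is taken, which suits the simple proportions in 8.3 poorly. List later SRS-related events separately, with follow-up time.

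**Attribution (7.2).** Record relationship to SRS/ablation separately from relationship to erlotinib, and let an event related to both appear in both tables.

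**Existing rate.** The pre-restart rate may stay if labelled as the immediate post-SRS assessment.

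**Reconciliation.** Sections 2.4.2, 4.3, 6.1 (footnote 2) and 6.9.1 differ on whether erlotinib is held around SRS and must be reconciled; this point takes no position on which is right.

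**Cost.** Wording changes, one more attribution entry per adverse event, and no new visits. There will be some overlap between tables, attribution will be less reliable where made retrospectively for patients already treated, and events after the fixed window will be reported only descriptively.

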## 3.0 PATIENT ELIGIBILITY

### 3.1 Inclusion Criteria

Subject must meet all of the inclusion criteria listed below to participate:

3.1.1 Written informed consent has been obtained.

3.1.2  $\geq 18$  years of age

3.1.3 Histologically or cytologically confirmed stage IV EGFR-mutant NSCLC or, in the absence of availability of EGFR testing (for example, inadequate tissue), clinical response overwhelmingly consistent with EGFR mutation (PR plus at least 6 months free of progressive disease as a consequence of EGFR-TKI therapy).

3.1.4 History of previous response to EGFR-TKI, defined as either a PR by RECIST1.1 criteria, or at least six months without progressive disease as a result of EGFR-TKI therapy

3.1.5 Progressive disease as measured via RECIST1.1 following EGFR-TKI therapy (with  $\leq 5$  sites of disease amenable to SRS or other locally-ablative treatment)

3.1.6 Eastern Cooperative Oncology Group (ECOG) performance status 0 or 1

3.1.7 Adequate organ and marrow function as defined below:

- Absolute neutrophil count [ANC]  $\geq 1,500$  cells/ $\mu$ L
- Hemoglobin  $\geq 10$  g/dL
- Platelets  $\geq 100,000$ / $\mu$ L
- Serum creatinine  $\leq 1.5$  mg/dL or calculated creatinine clearance  $\geq 60$  mL/min
- Total bilirubin  $\leq 3.0$  x upper limit of normal [ULN]

- Alanine aminotransferase [ALT]  $\leq 2.5 \times$  ULN
- Aspartate aminotransferase [AST]  $\leq 2.5 \times$  ULN

**3.1.8** Female patients must have a negative urine or serum pregnancy test at screening (pregnancy test not required for patients with bilateral oophorectomy and/or hysterectomy or for those patients who are > 1 year postmenopausal).

**3.1.9** All patients of reproductive potential must agree to use adequate contraception

[figure not shown]
### **3.2 Exclusion Criteria**

Subjects meeting any of the exclusion criteria listed below at baseline will be excluded from study participation:

- 3.2.1** Any unresolved chronic toxicities > grade 2, measured by CTCAE v4.
- 3.2.2** Treatment with any FDA approved or experimental cancer treatment following progression on EGFR-TKI (e.g., radiation or chemotherapy; supportive regimens such as denosumab or zoledronic acid will not result in exclusion)
- 3.2.3** Any history of previous  $\geq$  grade 3 toxicity attributable to erlotinib (except dermatological toxicity)
- 3.2.4** Pregnant or lactating female
- 3.2.5** Any previous radiation to sites of planned SRS. A patient may be deemed eligible in this case if a non-radiation mode of local ablation such as surgical resection is deemed safe and feasible by the PI.
- 3.2.6** History of another malignancy; **exception:** Subjects who have been disease-free for 3 years, or subjects with a history of completely resected non-melanoma skin cancer or successfully treated *in situ* carcinoma are eligible.
- 3.2.7** Concomitant anticancer therapy, immunotherapy, or radiation therapy (no radiation within prior 4 weeks)
- 3.2.8** Evidence of severe or uncontrolled systemic diseases (e.g., unstable or uncompensated respiratory, hepatic, renal, or cardiac disease)
- 3.2.9** Known hypersensitivity reaction or idiosyncrasy to erlotinib
- 3.2.10** Psychological, familial, sociological, or geographical conditions that do not permit compliance with the protocol
- 3.2.11** Any other concurrent condition that in the investigator's opinion would jeopardize compliance with the protocol

## 4.0 TREATMENT PLAN

### 4.1 Schema

The study will be a single arm non-randomized phase II study of forty patients. We anticipate completing accrual over a 2 year period.

### 4.2 Stereotactic Radiosurgery

All sites of progressive disease will be treated with SRS, unless an alternative locally ablative option is chosen. A maximum of five sites will be treated. If less than five sites have progressed on erlotinib, additional sites up to a total of 5 sites may be treated, at the discretion of the treating radiation oncologist. Guidelines for SRS will be defined by body site, consistent with standard of care radiation, as reviewed below.

#### 4.2.1 Radiosurgery Therapy: Brain

##### 4.2.1a Equipment

Modality: Gamma knife or X-rays with nominal energy of 4 megavoltage (MV) or greater for accelerator-based treatments, including isocentric conical collimators, mini-multi-leaf (5 mm or less) technology or linear accelerators mounted on robotic arms.

#### 4.2.1b Treatment technique

An immobilization/patient localization system is mandatory for this study. Multiple isocenter and non-isocentric techniques are permitted.

#### 4.2.1c Treatment volumes

The goal of treatment planning is to deliver a conformal dose of radiation to the contrast enhancing target volume based on MR or CT images. Treatment volumes will be determined based on correlation of diagnostic imaging with a treatment planning CT scan performed at 1.00 to 1.25mm slice thickness. Minimal margins are allowed of up to 3 mm will be used. Typically, no margin is used except in the setting of issues of indistinct borders. The relevant target volumes and critical structures for treatment planning will be contoured by the participating radiation oncologist and/or neurosurgeon. Both radiation oncologist and neurosurgeon need to review the target volumes. When a patient is able to undergo a MRI, MRI will be used with formal image registration. The preferred image is a T1 image post-gadolinium at a minimum of 3 mm between image slices. The MRI does not need to be performed in the treatment planning position.

The GTV is defined as the gadolinium-enhanced T1 image abnormality. In the setting of treating post-surgically, the tumor bed (resection cavity) as defined on the T1 gadolinium enhanced image will be treated. This can be termed GTV or CTV. No PTV will be defined unless there is evidenced of registration error. The use of a PTV will be at the discretion of the treating physicians but should not be greater than a 3 mm 3D expansion.

#### 4.2.1d Treatment schedule / time and dose considerations

Radiosurgery treatments will be delivered per institutional preference (on consecutive weekdays versus several per week; one fraction per day).

Time and dose considerations:

- *Prescription isodose:* The dose will be calculated to the 50-100% isodose curve as normalized to the maximum dose. Dose is specified in Gray (Gy) to muscle.
- *Coverage:* The target lesion should be covered at least 95% by the prescription isodose curve; small volume lesions (those treated with a single 5 mm collimator and have a high conformity (>1.8) index) may be covered with less than a 95% but not less than 90%
- *Conformity of dose:* Conformity indices  $PIV * TIV / TV^2$  should be within 1.00 – 1.80; small volume lesions (those treated with a single 5 mm collimator and have a high conformity (>1.8) index) may be treated with a conformity index < 2.0
- *Total dose:* The total dose is to the prescription isodose

- *Normal tissue dose limitations:* The dose to the optic chiasm and nerves will be < 8 Gy if a single fraction, < 15 Gy in 3 fractions, < 25 Gy in 5 fractions; if there has been prior radiation acceptable tolerance limits are < 6 Gy single fraction, < 12 Gy in 3 fractions, < 20 Gy in 5 fractions. Brainstem will be < 15 Gy per fraction or total cumulative dose of < 20 Gy unless tumor is intrinsic to the brainstem. Volume of brain receiving >12Gy should be limited to <10cc in a single fraction treatment. Volume of brain for fractionated treatment will not have a limit
- *Dose schedule:* Patients will receive one treatment daily, delivered per institutional preference (on consecutive days versus several per week; one fraction per day)

Max diameter of single tumor or volume	Fraction #	Total Dose (isodose prescription, NOT max dose)
<1 cm (<0.5cc)	1	20 Gy
1-2 cm (0.5 cc-4.2cc)	1	18-20 Gy
2-3 cm (4.2cc-14.1cc)	1 3	18 Gy 18-21 Gy
3-4.5 cm(14.1 cc-47.7 cc)	1 3	15 Gy 18-21 Gy
>4.5 cm (>47.7cc)*	5	25 Gy
*In general tumors greater than 6 cm or 133 cc should not be treated with stereotactic radiosurgery		

RTOG SRS QA Guidelines will be followed and AAPM Report 54 Guidelines will be followed

Please note: based on anatomic location, edema/mass effect, and patient's extracranial disease status doses can be reduced by 10% or converted to fractionated treatment. Normal tissue tolerance limits that are specified should be respected unless there are special circumstances.

Anatomic locations where dose reduction or fractionation can be considered are posterior fossa, deep and central (thalamic, insular, brainstem) or motor strip (or adjacent to motor strip). Dose reductions are allowed but not required. This will require clinical judgment.

Although we rarely treat more than 4 intracranial lesions, when doing so dose is 16 Gy to the lesions.

## 4.2.2 Radiosurgery Therapy: Chest and Lung

### 4.2.2a Equipment

Only photon (x-ray) beams produced by linear accelerators with photon energies of 4-10 MV will be allowed. Cobalt-60 and charged particle beams (including electrons, protons, and heavier ions) are not allowed. Photon beam energies  $> 10$  MV but not  $> 15$  MV will be allowed only for a limited number ( $\leq 2$ ) beams that must travel more than a cumulative distance of 10 cm through soft tissue (not lung) to reach the isocenter.

### 4.2.2b Treatment technique

Inverse treatment planning will be employed using isocentric and/or non-isocentric beam arrangements..

### 4.2.2c Treatment volumes

The goal of treatment planning is to deliver a conformal dose of radiation to the contrast enhancing target volume based CT images. Treatment volumes will be determined based on correlation of diagnostic imaging with a treatment planning CT scan performed at 1.00 to 1.50 mm slice thickness. Minimal margins of up to 3-10 mm will be used. The relevant target volumes and critical structures for treatment planning will be contoured by the participating radiation oncologist and/or thoracic surgeon. The preferred image for target contouring is a CT image post-contrast at a minimum of 1.5 mm between image slices with the image obtained at the normal end expiratory cycle. When a patient is unable to maintain a breath hold for the entire scan (which is an expected common occurrence) the breath hold at end expiration should be performed through the region where the tumor is located or the therapists can determine the optimal breath hold technique for compliance with the planning scan. If a breath hold technique cannot be performed a 4D-CT scan should be obtained.

Note: FOV on the “big bore” CT should be limited to 60 cm to avoid intentional artifact that may impact dose algorithm.

